Vitamin D is essential for mineral homeostasis and proper formation of bones⁵⁵. Deficiency of vitamin D is characterized by inadequate mineralization of bone and can present as rickets or osteomalacia. In addition, because the vitamin stimulates intestinal absorption of calcium and phosphorus, abnormalities in mineral homeostasis can occur. Vitamin D consists of several forms including vitamin D₂, vitamin D₃, 25 hydroxy-vitamin D, and 1,25 dihydroxy-vitamin D. Exposure of the skin to ultraviolet rays of the sun catalyzes the synthesis of vitamin D₃ from 7-dehydrocholesterol. Vitamin D₂ is synthesized from ergosterol in plants and is added to vitamin D supplemented milk. Vitamin D absorption occurs in the small intestine where it is then incorporated into chylomicrons and absorbed primarily via the lymphatics while a smaller amount is absorbed directly into the portal circulation. The liver catalyzes the hydroxylation of vitamin D₃ to 25 OH-vitamin D. In the kidney, 25-OH vitamin D is converted to 1,25 dihydroxy-vitamin D, which is the biologically active form of the vitamin.

There are many studies indicating that vitamin D malabsorption occurs in cholestasis⁵⁹⁻⁶². In a study with a small number of biliary atresia infants, baseline serum 25-OH vitamin D was deficient in 5/6 biliary atresia subjects after portoenterostomy with poor bile flow compared to 1/5 similar subjects with good bile flow. The peak change and area under the absorption curve for serum 25-OH vitamin D after administration of a one-time oral dose of 10 ug/kg 25-OH vitamin D₃ was significantly lower in all 11 biliary atresia subjects compared to 5 pediatric controls⁶². The 25-OH vitamin D levels in 4 infants with biliary atresia did not increase after supplementation with 2000 IU by mouth of vitamin D₂ for 2 weeks compared to 7 infants with neonatal hepatitis or 9 normal controls⁶⁰. In an oral 25-OH vitamin D₃ tolerance test, the mean increase in serum 25-OH vitamin D for 5 non-jaundiced biliary atresia subjects after portoenterostomy was significantly greater (48.9 ± 30.6 ng/ml versus 23.7 ± 9.5 ng/ml) in jaundiced subjects⁶³. The absorption of vitamin D₃ 1000 IU/kg was enhanced in 8 cholestatic children when given with the water miscible form of vitamin E (TPGS, 25 IU/kg) compared to when vitamin D was given alone⁶⁴.

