The fat-soluble vitamin requirements in infants with cholestasis remain unclear. The findings in most studies on fat-soluble vitamin absorption have been limited by small groups of infants. Furthermore, the requirements may vary depending on the degree of cholestasis and the primary disease. We propose to closely assess the efficacy of a formulation of fat-soluble vitamins commonly used in clinical practice by following levels of fat-soluble vitamins in both corticosteroid-treated and placebo groups. The preparation contains vitamin E in the water miscible form (TPGS), which has also been shown to improve the absorption of vitamin D⁶⁴ and theoretically enhances the absorption of the other fat-soluble vitamins. We will use the dose of 2 milliliters of vitamin solution as the starting dose for this study. This dose is based on higher requirements for infants with cholestasis than the Recommended Daily Allowances (RDA) (see Table 7 below). In addition, based on clinical experience in dosing fat-soluble vitamins in this population, additional vitamin K will be necessary, and will consist of 2.5 mg by mouth to be given three times a week. In addition to vitamins A, D, E and K, the AquADEK® vitamin formulation includes water-soluble vitamins and minerals. There is a paucity of information regarding water-soluble vitamin status of infants with cholestasis. Data from adult patients with chronic liver disease suggested that B vitamin deficiency may exist in patients with cholestasis⁷¹. In addition, low plasma zinc levels have been reported in infants awaiting liver transplantation⁷²; an adequate zinc status is necessary for the synthesis and secretion of RBP.

Table 7. The Pediatric Liquid Formulation of AquADEK® and the RDA for Infants.

Vitamin	RDA		2 ml AquADEK®	Amount x RDA	
	0-0.5 yr	0.5-1yr		0-0.5 yr	0.5-1 yr
Vitamin A (palmitate and beta carotene)	375 ug	400 ug	*1902 ug	5.1 x	4.9 x
Vitamin D (cholecalciferol)	7.5 ug	10 ug	*20 ug	2.7 x	2.0 x
Vitamin E (TPGS)	3 mg	4 mg	*54 mg	18 x	13.5 x
Vitamin K (phytonadione)	5 ug	10 ug	200 ug	40 x	20.0 x
Vitamin C (ascorbic acid)	30 mg	35 mg	90 mg	3.0 x	2.6 x
Vitamin	RDA		2 ml AquADEK®	Amount x RDA	
	0-0.5 yr	0.5-1yr		0-0.5 yr	0.5-1 yr
Thiamine (Vitamin B ₁)	0.3 mg	0.4 mg	1 mg	3.3 x	2.5 x
Riboflavin (Vitamin B ₂)	0.4 mg	0.5 mg	1.2 mg	3.0 x	2.4 x
Niacin (niacinamide)	5 mg	6 mg	12 mg	2.4 x	2.0 x
Vitamin B ₆ (pyridoxine)	0.3 mg	0.6 mg	1.2 mg	4.0 x	2.0 x
Vitamin B ₁₂	0.3 ug	0.4 ug	8 ug	26.7 x	20.0 x

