Using the same definition of good bile drainage as in the primary hypothesis, the duration of time with good bile drainage (time to onset of poor bile drainage, transplant or death, whichever comes first) will be modeled by Cox proportional hazards model using the same model as above. If there is a statistically significant difference, the profiles of the bilirubin for the two treatment groups will be compared and 95% confidence limits will be computed.

Aim 2: To determine whether corticosteroid treatment after portoenterostomy will improve outcome as defined by survival without transplantation at 24 months of age.

Hypothesis 2: Survival without liver transplantation will be greater at 24 months of age in infants treated with corticosteroids than in those treated with placebo.

A Cox proportional hazards model will be fitted to the time to transplant or death. The same covariates will be included in the model as for the previous hypothesis.

Aim 3: To determine whether corticosteroid treatment after portoenterostomy will improve growth of infants with biliary atresia.

Hypothesis 3: Weight and height Z-scores at 12 and 24 months of age will be higher in the infants treated with corticosteroids than in those treated with placebo.

The weight and height Z-scores at 12 and 24 months of age will each be modeled by a random effects model with the same covariates as above.

Aim 4: To determine whether corticosteroid treatment improves biochemical indicators of each of the fat-soluble vitamins after supplementation with standard doses.

Hypothesis 4a: Treatment with corticosteroids leads to improved bile drainage (hypothesis 1) which, in turn, increases the probability that an infant will achieve vitamin sufficiency of each of the fat-soluble vitamins following supplementation of AquADEK®.

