Each vitamin will be analyzed separately. For hypothesis 4a, each subject will be classified as having achieved or not achieved vitamin sufficiency, first with supplementation and then without supplementation. Vitamin sufficiency will be defined as having achieved the target concentration ranges specified in Section 4.N8. Although we can model the outcome as a function of treatment group, the underlying hypothesis is that the outcome is a function of bilirubin level. Therefore, we will model the outcome by logistic regression using bilirubin as a surrogate for bile drainage; bilirubin may be included in the model either as a continuous measure or as a dichotomy where <1.5 mg/dL is defined as good bile flow and ≥ 1.5 mg/dL as inadequate bile flow. Gender and race of the infant, presence of major congenital anomalies, as well as site as a random effect will be included as covariates.

Hypothesis 4b: Treatment with corticosteroids leads to improved bile drainage (hypothesis 1) which, in turn, reduces the dose required for supplementation and the length of time of supplementation for each of the fat-soluble vitamins.

As in hypothesis 4a, each vitamin will be analyzed separately. There are two components to this hypothesis. The first is the total amount of supplementation and the second is the length of supplementation. We will compute the total amount of supplementation up to 6 months of age as the first dependent variable and the time to achieving target concentrations without supplementation as the second dependent variable. The first variable (after transformation) will be analyzed by a random effects model with bilirubin as the independent variable and the same covariates as in hypothesis 4a. The second variable will be modeled by Cox regression with the same independent variable and covariates.

Aim 5: To determine whether corticosteroid treatment after portoenterostomy will decrease the incidence of persistent ascites or ascites that requires medical treatment.

Hypothesis 5: The incidence of ascites will be decreased at 12 and 24 months of age in infants treated with corticosteroids than in those treated with placebo.

Similar to hypothesis 2, a Cox proportional hazards model will be fitted to the time to diagnosis with ascites.

Other endpoints will be analyzed similarly depending on whether they are continuous, dichotomous or time-to-event.

5.C. Data Management

5.C1. Case Report Forms

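### Aim 4 asks whether corticosteroids improve vitamin status, but the models for Hypotheses 4a and 4b test bilirubin, contain no treatment term and are not tied to the Hypothesis 1 result

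*Protocol*

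**What the plan says.** Section 5.B states Aim 4 as a treatment question: "To determine whether corticosteroid treatment improves biochemical indicators of each of the fat-soluble vitamins after supplementation with standard doses". Hypotheses 4a and 4b are worded as a chain. Corticosteroids improve bile drainage, with a cross-reference to Hypothesis 1, and better drainage then improves vitamin sufficiency (4a) or reduces the dose and duration of supplementation (4b).

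For 4a the section says "Although we can model the outcome as a function of treatment group, the underlying hypothesis is that the outcome is a function of bilirubin level", and continues: "Therefore, we will model the outcome by logistic regression using bilirubin as a surrogate for bile drainage". The adjustment set is short: "Gender and race of the infant, presence of major congenital anomalies, as well as site as a random effect will be included as covariates".

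For 4b, the total amount of supplementation "will be analyzed by a random effects model with bilirubin as the independent variable and the same covariates as in hypothesis 4a". Time to reaching target concentrations without supplementation goes into a Cox regression with the same independent variable and covariates. Treatment group is in none of the three models.

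Two other places bear on this. Section 4.N6 describes "following levels of fat-soluble vitamins in both corticosteroid-treated and placebo groups", which points to a comparison of arms. Section 5.A2 says that there are no data for a power calculation on vitamin sufficiency.

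**The concern.** The bilirubin coefficient compares infants who drained well with infants who did not, whichever arm they were in. Bilirubin is measured after randomisation, so the comparison is not protected by it. Infants with good drainage may differ in age at surgery, disease severity and much else. A clear bilirubin coefficient is what the physiology in 4.N and 4.N1 would lead one to expect even if corticosteroids had no effect.

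For 4b the association is partly built in. Section 4.M4 allows the vitamin supplements to be stopped once total bilirubin is below 1.5 mg/dL, so the amount and duration of supplementation follow bilirubin through the protocol's own rule.

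At stake is what can be said under Aim 4. Its hypotheses open with the effect of corticosteroids, yet the analysis assigned to them yields no estimate of that effect. A reader of the results could take a significant coefficient as evidence for the treatment claim.

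**Working it through.** **Specification, set side by side (section 5.B)**

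| Hypothesis | Tested term | Treatment group in model? |
|---|---|---|
| 1a | treatment-group coefficient, stated explicitly | yes |
| 1b, 2, 3 | reuse the 1a model or its covariates | yes |
| 4a, logistic | bilirubin | no |
| 4b, amount, random effects | bilirubin | no |
| 4b, time, Cox | bilirubin | no |

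No mediation analysis is specified, and no sentence makes an Aim 4 conclusion conditional on a significant Hypothesis 1 result. The protocol gives no numerical claim for Aim 4, so there is no figure to reproduce.

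**Illustration of size**

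Inputs from the protocol (5.A.1): good drainage 50% on control and 75% as the goal; two-sided 5% test; 140 infants with up to 20% attrition, so 140 × 0.80 = 112, or 56 per arm.

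Inputs that are assumptions: the proportion vitamin-sufficient with good and with poor drainage. The protocol gives none for its own regimen. Three pairs are used:
- 80% and 17%, borrowed from a small vitamin D study in 4.N3, where "baseline serum 25-OH vitamin D was deficient in 5/6 biliary atresia subjects after portoenterostomy with poor bile flow compared to 1/5 similar subjects" with good flow. Sufficient is then 4/5 = 80% and 1/6 = 17%.
- 75% and 45%.
- 75% and 55%.

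Method: 40,000 simulated trials per row. Sufficiency depends only on drainage. Each trial has a pooled two-proportion z test by bilirubin group and another by treatment group, without covariates. Only 4a is simulated.

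*No steroid effect (50% good drainage in both arms):*

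| Sufficiency, good / poor | Bilirubin test significant | Treatment test significant | Bilirubin test and Hypothesis 1 both significant |
|---|---|---|---|
| 80 / 17% | 100% | about 5% | about 5% |
| 75 / 45% | 91% | about 5% | about 4% |
| 75 / 55% | 61% | about 5% | about 3% |

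Hand check of the middle row, about 56 infants per bilirubin group: difference 0.30; null SE = √(0.60 × 0.40 × 2/56) = 0.0926; SE under the alternative = √((0.75 × 0.25 + 0.45 × 0.55)/56) = 0.0881. Power = Φ((0.30 − 1.96 × 0.0926)/0.0881) = Φ(1.35) = 0.91.

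*Full hoped-for effect (50% against 75% good drainage), treatment-group test:*

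| Sufficiency, good / poor | Control arm | Steroid arm | Power |
|---|---|---|---|
| 80 / 17% | 48.3% | 64.2% | 38% |
| 75 / 45% | 60.0% | 67.5% | 13% |
| 75 / 55% | 65.0% | 70.0% | 9% |

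The arm rates are weighted averages. In the middle row the control arm is 0.5 × 75 + 0.5 × 45 = 60.0% and the steroid arm is 0.75 × 75 + 0.25 × 45 = 67.5%. The arm difference is only a quarter of the gap between drainage groups: 0.25 × 30 = 7.5 points.

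A separate run with 114 infants and other assumed pairs (70/50, 80/50, 80/40 and 90/40%) gave 59 to 100% for the bilirubin test under no steroid effect, and again about 5% for the treatment test.

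**The case against.** The strongest defence is the wording of the hypotheses. They describe two links, and the first is handed to Hypothesis 1, where 1a tests the treatment coefficient. If corticosteroids do nothing, Hypothesis 1 will usually fail and the chain is visibly broken. Requiring both links to be significant gives a false-positive rate of about 3 to 5%. This stands as far as it goes, but the protocol does not write that requirement down. Even when both links are significant, a drainage effect plus an observational association does not estimate the arm difference that Aim 4 asks about.

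Two stronger readings are tempting, and the document does not support them:

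- A reader might infer that Aim 4 would be falsely confirmed in 60 to 100% of trials. Those rates are not a type I error. They are power to detect a bilirubin–vitamin association that was put into the simulation, and they become false confirmations only if Hypothesis 1 is ignored.
- A reader might infer that vitamin status is never compared between arms. INR is the named vitamin K marker in 4.E, and INR and PIVKA-II carry treatment-arm hypotheses among the tertiary endpoints in 5.A.3. That section calls those analyses hypothesis-generating, but an arm comparison is envisaged for vitamin K. The gap is in the 4a and 4b models.

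The assumed rates are also soft. The 80/17% pair rests on 11 infants, one vitamin and a baseline level, whereas in this trial deficient infants have doses adjusted and rechecked (4.N9, 4.N10), which may narrow the gap. The bilirubin models do answer a question that 4.N poses. Leaving open whether bilirubin enters as continuous or dichotomous is a detail for an analysis plan and is not an error.

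**Conclusion.** The mismatch between Aim 4 and its models is real. The protocol names the treatment-group model and chooses another, so this is a stated choice and not a detail left to a later plan. The three specified models test whether bile drainage relates to vitamin status. They do not test whether corticosteroids change it, and for 4b the relation partly follows from the supplementation rule.

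The size is illustrative. With no steroid effect, the bilirubin test is significant in about 60 to 100% of trials and a treatment-group test in about 5%. These figures rest on assumed sufficiency rates, an unadjusted test and the 4a outcome only. The direction does not depend on the particular rates, provided that drainage and sufficiency are related, as the protocol itself expects.

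This should be fixed but is not critical. It touches one secondary aim for which no power is claimed. The primary analysis and the sample size are unaffected.

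**What to change.** In section 5.B, Aim 4:

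1. Make treatment group the tested term for 4a (logistic) and for both parts of 4b (random effects and Cox), with the Hypothesis 1a covariates and site as a random effect.
2. Report the arm difference with its 95% CI, for each vitamin, as the Aim 4 result.
3. Keep the bilirubin models, labelled as supportive analyses of mechanism, preferably also adjusted for age at portoenterostomy and baseline bilirubin, which the 1a model already includes.

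This changes wording only and needs no new data or visits. The price is that Aim 4 will more often be inconclusive: the arm comparison has about 9 to 38% power under the assumed rates even if drainage improves from 50% to 75%. Since 5.A2 claims no power for this endpoint, no promise is broken, and the confidence interval will show how much the trial can say.

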Hypothesis 2: Survival without transplantation will be greater at 24 months of age in infants treated with corticosteroids than those treated with placebo.

Aim 3: To determine whether corticosteroid treatment after portoenterostomy will improve growth of infants with biliary atresia.

Hypothesis 3: Weight and height Z-scores at 12 and 24 months of age will be greater in the infants treated with corticosteroids than those treated with placebo.

Aim 4: To determine whether corticosteroid treatment improves biochemical indicators of each of the fat-soluble vitamins after supplementation with standard doses.

Hypothesis 4a: Treatment with corticosteroids leads to improved bile drainage (hypothesis 1) which, in turn, increases the probability that an infant will achieve

vitamin sufficiency of each of the fat-soluble vitamins following supplementation of AquADEK®.

Hypothesis 4b: Treatment with corticosteroids leads to improved bile drainage (hypothesis 1) which, in turn, reduces the dose required for supplementation and the length of time of supplementation for each of the fat-soluble vitamins.

Aim 5: To determine whether corticosteroid treatment after portoenterostomy will decrease the incidence of persistent ascites or ascites that requires medical treatment.

Hypothesis 5: The incidence of ascites will be decreased at 12 and 24 months of age in infants treated with corticosteroids than those treated with placebo.

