When the total bilirubin is ≥ 1.5 mg/dL and the child is less than 12 months of age, MCT-containing formula or breast milk should be used, as long as the child's growth is "adequate". When the total bilirubin is < 1.5 mg/dL, the child can be transitioned to standard infant formula (if < 1 year of age) and whole milk (if ≥ 1 year of age). MCT-containing formula will be continued until 24 months of age if the total bilirubin is ≥ 1.5 mg/dL and the child is over 12 months of age. When growth is inadequate, measures will be taken for nutritional rehabilitation according to medical management used at each ChiLDREN clinical center.

4.M4. Vitamin Supplementation

All cholestatic subjects with total bilirubin ≥ 1.5 mg/dL will receive:

- AquADEK® vitamin drops: 2 ml orally per day until 2 years of age
- Vitamin K : 2.5 mg orally coadministered with AquADEK® vitamin drops on Mondays, Wednesdays and Fridays

AquADEK® and Vitamin K may be stopped when the total bilirubin is < 1.5 mg/dL. Serum vitamin levels and prothrombin time/INR will be measured during the follow-up visit at one month after portoenterostomy. When an abnormal value is obtained, the dosage of the specific vitamin will be augmented or reduced, as appropriate, and the level will be rechecked in 4 weeks (see Section 4N, below).

4.M5. Ursodeoxycholic Acid

- Ursodeoxycholic acid (Urso 250® or Actigall®): 20 mg/kg/day divided BID orally until 2 years of age.

Ursodeoxycholic acid will be discontinued if serum total bilirubin is > 15 mg/dL to avoid potential toxicity.

4.M6. Antibiotics for Prophylaxis Against Ascending Cholangitis

- TMP/SMZ: 4-5 mg TMP/kg/day orally for 6 months

If the subject has evidence of decreased renal function as indicated by an elevated serum level of creatinine, we will adjust the dose of TMP/SMZ for renal insufficiency. For serum creatinine > 1.0 to 1.5 mg/dL, the dose will be reduced by 25%; for creatinine > 1.5 to 2.5 mg/dL, the dose will be reduced by 50%; and for serum creatinine > 2.5 , the subject will be withdrawn from the study. These adjustments are based on a normal serum creatinine of < 0.6 mg/dL in the first year of life.

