Two central laboratories will be measuring vitamin levels for this study. A sample will be sent to the Pediatric CTSC Core Laboratory at The Children's Hospital in Denver which will perform all the tests except the PIVKA-II. The samples that are sent to Denver will be identified with the following personal health information: child's name, medical record number, and date of birth. The child's unique study code will not be shared. It is necessary for this information to be collected and shared because these are clinically indicated tests that will be reported to the site. These tests will be paid by the study.

PIVKA-II samples will be barcoded and sent to the NIDDK Repository . The NIDDK Repository will then batch ship these samples to Cincinnati Children's Hospital Medical Center for processing. The NIDDK Repository will verify which samples were sent to Cincinnati, and Cincinnati will send the results to the DCC. PIVKA-II is not being used clinically by the sites and these results will not be reported back to the site. These tests will be paid by the study.

Target vitamin levels:

- Vitamin A: A molar ratio of retinol:RBP will be used to assess vitamin A nutriture. A cut-off of 0.8 mol/mol will be used to define vitamin A deficiency. If a retinol:RBP ratio is below 0.8 and serum retinol is less than 20 ug/dl, the subject will be considered vitamin A deficient and supplementation will be recommended (see below). If the serum retinol is <20 ug/dl and the retinol:RBP ratio is >0.8, vitamin A status will be reassessed in one month. If the serum retinol is > 20 ug/dl and the ratio is < 0.8, vitamin A status will be reassessed in one month. If the serum retinol is greater than the upper limit of normal range, the vitamin A dose will be decreased by 50% and vitamin A status reassessed in one month.
- Vitamin D: The target serum 25-OH vitamin D concentration range is 15-45 ng/ml.
- Vitamin E: The target serum vitamin E:lipid ratio will be >0.6 mg/g in children less than 12 months of age and >0.8 mg/g in children older than 12 months of age. The upper limit of vitamin E:total lipids ratio will be 3.5 mg/g.
- Vitamin K: The INR will be used as surrogate marker of vitamin K status with a target INR<1.2

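### The Aim 4 vitamin models use bilirubin in place of treatment group, so this secondary aim has no randomised comparison

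*Protocol*

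**What the plan says.** Section 1 states Aim 4 as a treatment question: "To determine whether corticosteroid treatment improves biochemical indicators of each of the fat-soluble vitamins after supplementation with standard doses". Section 4.E lists the vitamin biomarkers among the secondary outcomes. Hypotheses 4a and 4b are worded as a chain: steroids improve drainage (Hypothesis 1), and better drainage then raises vitamin sufficiency (4a) and lowers the dose and duration of supplementation (4b).

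For 4a, section 5.B grants that the outcome could be modelled on treatment group but sets this aside because "the underlying hypothesis is that the outcome is a function of bilirubin level". It continues: "Therefore, we will model the outcome by logistic regression using bilirubin as a surrogate for bile drainage". The adjustment set is: "Gender and race of the infant, presence of major congenital anomalies, as well as site as a random effect will be included as covariates". For 4b it says "We will compute the total amount of supplementation up to 6 months of age as the first dependent variable". That dose is modelled on bilirubin with the 4a covariates, and so is the Cox model for time to reaching target without supplements.

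Section 4.M4 gives the supplements to infants with total bilirubin of 1.5 mg/dL or more, and says they "may be stopped when the total bilirubin is < 1.5 mg/dL".

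**The concern.** The aim is about treatment, but the regressor is a measurement taken after randomisation. Infants with low bilirubin after surgery differ from those with high bilirubin in ways that randomisation does not balance. The Hypothesis 1a model adjusts for two obvious candidates, baseline bilirubin and age at portoenterostomy, and the Aim 4 models drop both. The bilirubin coefficient is therefore an observational association, and its size does not depend on whether steroids work.

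Two features of the plan weaken it further. The supplementation rule uses the same 1.5 mg/dL threshold that 5.B offers for dichotomising bilirubin, so dose and time to coming off supplements are partly tied to the regressor by design. The dose total also stops at 6 months of age, so an infant operated on later has less time to accumulate dose whatever happens to bile flow.

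At stake is a secondary aim of a randomised trial that would be reported without a randomised comparison. The primary test is not affected.

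**Working it through.** **1. Models compared (section 5.B).**

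| Hypothesis | Tested or independent variable | Treatment group in model | Baseline bilirubin and age at surgery |
|---|---|---|---|
| 1a | treatment group | yes | yes |
| 1b, 2, 3 | same model or covariates as above | yes | yes |
| 4a | bilirubin | no | no |
| 4b, dose | bilirubin | no | no |
| 4b, Cox | bilirubin | no | no |

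**2. Inputs.** The protocol gives no figure for Aim 4; section 5.A2 says there are no data for power on the vitamin endpoints. The primary-endpoint inputs in 5.A.1 are 50% versus 75% good drainage, two-sided 5% and 80% power. With unpooled variance, n per arm = (0.50×0.50 + 0.75×0.25)(1.960 + 0.842)²/0.25² = 0.4375×7.85/0.0625 ≈ 55. That is 110 in total, as stated. This check only confirms the inputs.

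Evaluable N is 140×0.8 = 112 (20% attrition) or 140. Sufficiency rates by drainage are assumptions: 70/50, 80/50 and 80/40% (good/poor). A fourth pair comes from the vitamin D study in section 4.N3, with deficiency in 1/5 good-flow and 5/6 poor-flow infants, hence sufficiency of about 80/17%.

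**3. Simulation.** There were 20,000 trials per setting, using Pearson chi-square at 5%, with bilirubin dichotomised and sufficiency depending only on drainage. The 80/17 row was checked with the two-proportion power formula as well.

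Percentage of trials significant at N=112:

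| Sufficiency good/poor | Bilirubin term, steroids inert (50/50) | Bilirubin term, steroids effective (50/75) | Treatment term, inert | Treatment term, effective |
|---|---|---|---|---|
| 70/50 | 58 | 57 | 5 | 8 |
| 80/50 | 92 | 91 | 5 | 14 |
| 80/40 | 99 | 99 | 5 | 20 |
| 80/17 | about 100 | about 100 | about 5 | 39 |

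At N=140 with inert steroids, the bilirubin term is significant in 68, 97 and over 99% for the first three rows. The treatment term with effective steroids reaches 9, 16, 24 and 47%. If bilirubin and sufficiency are unrelated (60/60), the bilirubin term rejects about 5%.

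The treatment contrast is weak because the effect is diluted through drainage. For 80/50, arm sufficiency is 0.50×80 + 0.50×50 = 65% on placebo and 0.75×80 + 0.25×50 = 72.5% on steroids.

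**4. Joint reading.** Suppose Aim 4 is called confirmed only if the treatment effect on drainage and the bilirubin-vitamin link are both significant. With inert steroids this happens at roughly 0.05×0.58 ≈ 3% to 0.05×0.99 ≈ 5%. Simulation of the joint event gave about 3-5% at both sample sizes.

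**5. Exposure time in 4b.** Taking 6 months of age as 183 days, time available is 183 minus age at surgery. Surgery at day 30 leaves 153 days and surgery at day 120 leaves 63, a ratio of 2.4. These ages are illustrative, but section 4.M1 does provide for surgery at 4 months or later.

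**The case against.** The strongest defence is that 4a and 4b are written as a chain through Hypothesis 1. The first link is tested by randomised treatment group under Aim 1, and section 5.B supplies the second. Read together, the two tests would both be significant only about 3-5% of the time with inert steroids. A reader might infer from the 58-99% figures that Aim 4 would be confirmed even if steroids did nothing. The document does not support that: those figures are power to detect an assumed, real bilirubin-vitamin association, not a false-positive rate for the aim. This part of the defence stands. But the protocol states no joint rule, and two significant links do not estimate the effect of randomised treatment on vitamins.

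The protocol is also not wholly without treatment comparisons. Section 4.N6 follows vitamin levels in both groups. Section 5.A.3 hypothesises lower INR and PIVKA-II on steroids, and INR is the vitamin K marker. This helps for vitamin K, but it supplies no test for vitamins A, D and E or for 4b.

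Three further inferences are tempting and should not be drawn:

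- **Dose wholly set by bilirubin.** Stopping below 1.5 mg/dL is permitted, not required, and sections 4.N9 and 4.N10 adjust individual vitamins on measured levels. The dependence is partial.
- **Separation in the off-supplement models.** Nothing in the document establishes quasi-complete separation, and it was not computed.
- **Above-range values as an error.** 5.B says "Vitamin sufficiency will be defined as having achieved the target concentration ranges specified in Section 4.N8", and for vitamin D "The target serum 25-OH vitamin D concentration range is 15-45 ng/ml". Only vitamin D has a plainly two-sided target; the vitamin E upper limit is stated apart from its target. Section 4.N9 treats above-range values as needing adjustment, so counting them as success would be a preference, not a correction.

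Finally, the aim carries no power claim, and the treatment comparison would itself be weak.

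**Conclusion.** The point holds in a limited form. As specified, the 4a and 4b models give no randomised comparison for a secondary aim that is worded as a treatment question. This is not a detail left open for an analysis plan, because the protocol names the treatment model and chooses another. The bilirubin result would be nearly the same in both worlds (58-99% versus 57-99% significant at N=112), so it carries almost no information on the steroid effect.

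The size rests on assumed sufficiency rates, on vitamins responding only through drainage, and on unadjusted tests of dichotomised bilirubin. It also needs bilirubin and vitamin status to be associated, which sections 4.N and 4.N3 lead one to expect. The mismatch between aim and model needs none of these assumptions. It should be fixed, but the primary analysis does not depend on it.

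**What to change.** In section 5.B, Aim 4:

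- Make randomised treatment group the tested term in the 4a logistic model and in both 4b models (dose and Cox), with the Hypothesis 1a covariates, including baseline bilirubin and age at portoenterostomy.
- Keep the bilirubin models, labelled as supportive mechanistic analyses.
- Total the supplement dose over a fixed period after portoenterostomy instead of to 6 months of age, so that the length of the window does not depend on age at surgery.
- State that the treatment comparison has low power (about 8-24% under the assumed rates and 39-47% at the cited vitamin D rates, for N of 112 to 140) and that no power is claimed for these endpoints. A non-significant result should then not be read as absence of effect.

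The cost is wording only, with no new data or visits. The downside is that the treatment test will often be inconclusive, but it answers the stated aim.
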